8.0 Statistical Methods and Determination of Sample Size

8.1 Statistical and Analytical Plans

The primary analysis will occur after all subjects have completed the PT Week 12 Visit or prematurely discontinued the study. The data for the primary analysis will be locked after data cleaning. Data after PT Week 12 will be added to a new version of the database which will be cleaned and locked at the end of the study. An interim analysis may be conducted for the purpose of regulatory interaction.

SAS[®] (SAS Institute, Inc., Cary, NC) for the UNIX operating system will be used for all analyses. All confidence intervals will be two-sided with an alpha level of 0.05.

Descriptive statistics will be provided, such as the number of observations (N), mean, and standard deviation (SD) for continuous variables and counts and percentages for discrete variables.

Safety, and demographic analyses will be performed on all subjects who receive at least one dose of study drug. Analyses, as specified in the statistical analysis plan, will be presented by treatment arm and overall. Efficacy analyses will be performed on the intent-to-treat (ITT) population defined as all enrolled subjects who receive at least one dose of study drug, unless otherwise specified. Sensitivity analyses of the primary efficacy endpoint, when applicable, will be performed on the intention-to-treat population modified to exclude subjects who did not achieve SVR₁₂ for reasons other than virologic failure (mITT-VF).

No data will be imputed for any efficacy or safety analysis except for analyses of SVR endpoints (HCV RNA data). HCV RNA values will be selected for the analyses of all SVR endpoints (e.g., SVR₄, SVR₁₂, and SVR₂₄) based on defined visit windows. A backward imputation method will be used to impute missing responses for SVR analyses.

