4.2 Design Diagram

Study M15-942 is a Phase 3b, open-label, non-randomized, multicenter study to evaluate the efficacy and safety of ABT-493/ABT-530 in combination with SOF and RBV in HCV GT1 – 6 infected subjects, including subjects with compensated cirrhosis and/or HIV-1 co-infection and/or post-liver or post-renal transplant, who have experienced virologic failure while participating in an AbbVie HCV parent study.

It is anticipated that approximately 50 HCV-infected subjects who have experienced virologic failure following treatment with regimens containing ABT-493/ABT-530, 3D or 2D in one of the AbbVie HCV parent studies will be enrolled. Subjects will be allocated to the 12-week treatment duration (Arm A) or the 16-week treatment duration (Arm B) based on HCV GT, cirrhosis status, and treatment experience with PI and/or NS5Ai-containing regimens prior to enrolling in the AbbVie HCV parent studies, as defined in [Table 1](#).

Table 1. Treatment Arm Allocation in Study M15-942

Patient Population			
Genotype**	Cirrhotic Status*	PI and/or NS5Ai-Experienced Prior to the AbbVie HCV Parent Study	Study M15-942 Treatment Arm
1, 2, 4, 5 and/or 6	NC	No	A
3	Any	Any	B
Any	C	Any	B
Any	Any	Yes	B

* NC = non-cirrhotic; C = cirrhotic

** If the subject's HCV GT at Screening is unknown, or if it is mixed and includes GT3, then the subject will be assigned to Arm B (16 weeks), regardless of the cirrhosis status or PI and/or NS5Ai use prior to the AbbVie HCV Parent Study.

Arm A will enroll approximately 5 subjects, and Arm B will enroll approximately 45 subjects. Subjects will receive ABT-493/ABT-530 300 mg/120 mg QD, SOF 400 mg QD, and RBV 600 to 1200 mg daily in two divided doses, orally, for 12 (Arm A) or 16 (Arm B) weeks (Figure 1). Dosing of RBV will be based on baseline age and weight as defined in Table 2.

Scheduled visits for subjects in the Treatment Period consist of Day 1 and Weeks 2, 4, 8, and 12 for all subjects and an additional Week 16 visit for subjects in Arm B. Subjects who complete or prematurely discontinue study drug will be followed for 24 weeks. During the Post-Treatment Period, all subjects will have visits at Post-Treatment Weeks 4, 12, and 24.

Figure 1. Study Schematic

[figure not shown]

Table 2. Ribavirin Dosing Recommendations

Age at Baseline (Years)	Body Weight at Baseline (kg)	Daily Dose (mg)	Number of 200 mg Tablets Per Period of the Day
≥ 18	< 75	1000	5 tablets
	≥ 75	1200	6 tablets
≥ 12 and < 18	35 – 46	600	3 tablets

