4.3 Sample Size

This study serves to provide data on using ABT-493/ABT-530 in combination with SOF and RBV as a retreatment option for subjects infected with HCV GT1 – 6 who experienced virologic failure following treatment with regimens containing ABT-493/ABT-530 or 3D or 2D. No formal hypothesis will be tested in this study. The sample size of this study is determined based on the projected number of virologic failures in AbbVie HCV parent studies.

The two-sided 95% confidence intervals (CIs) based on Wilson's score method¹ for a given number of failures are shown in [Table 3](#) for Arm A, B, and overall. The Wilson's score method is expected to be used instead of the normal approximation method because the number of SVR₁₂ non-responders is expected to be less than 5 (see [Section 10.3](#)).

Table 3. The 95% CIs Using the Wilson's Score Method for a Given Number of Failures

Number of failures for Arm A, B, or overall	Arm A (N = 5)	Arm B (N = 45)	Overall (N = 50)
0	(56.6%, 100.0%)	(92.1%, 100.0%)	(92.9%, 100.0%)
1	(37.6%, 96.4%)	(88.4%, 99.6%)	(89.5%, 99.6%)
2	(23.1%, 88.2%)	(85.2%, 98.8%)	(86.5%, 98.9%)
3	(11.8%, 76.9%)	(82.1%, 97.7%)	(83.8%, 97.9%)
4	(3.6%, 62.4%)	(79.3%, 96.5%)	(81.2%, 96.8%)

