5.1.2 Modified Intention-to-Treat (mITT) Populations

Sensitivity analyses of SVR₁₂ as described in Section 10.5, when applicable, will be performed on the ITT population modified to exclude subjects who do not achieve SVR₁₂ for reasons other than virologic failure (mITT-VF).

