SVR₄ = HCV RNA < LLOQ in the SVR₄ window (4 weeks after the last actual dose of study drug) without any confirmed quantifiable (\geq LLOQ) post-treatment value before or during that SVR window.

SVR₁₂ = HCV RNA < LLOQ in the SVR₁₂ window (12 weeks after the last actual dose of study drug) without any confirmed quantifiable (\geq LLOQ) post-treatment value before or during that SVR window.

SVR₂₄ = HCV RNA < LLOQ in the SVR₂₄ window (24 weeks after the last actual dose of study drug) without any confirmed quantifiable (\geq LLOQ) post-treatment value before or during that SVR window.

Relapse₁₂ = confirmed HCV RNA \geq LLOQ between end of treatment and 12 weeks after last actual dose of study drug (up to and including the SVR₁₂ window) for a subject with HCV RNA < LLOQ at Final Treatment Visit who completed treatment, excluding reinfection as described below.

Relapse₂₄ = confirmed HCV RNA \geq LLOQ within the SVR₂₄ window for a subject who achieved SVR₁₂ and has HCV RNA data available in the SVR₂₄ window, excluding reinfection.

Relapse_{overall} = confirmed HCV RNA \geq LLOQ between end of treatment and up to and including the last HCV RNA measurement collected in the Post-Treatment Period for a subject with HCV RNA < LLOQ at Final Treatment Visit who completed treatment, excluding reinfection.

Virologic failure = On-treatment virologic failure or Relapse_{overall}

Only subjects who have at least one post-treatment HCV RNA value will be included in analyses of relapse. For the analysis of relapse, completion of treatment is defined as any subject with study drug duration of 77 days or greater for Arm A and 103 days or greater for Arm B. If the last available post-treatment value is \geq LLOQ, then the subject will be considered a relapse (i.e., will not require confirmation).

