HCV reinfection is defined as confirmed HCV RNA \geq LLOQ after the end of treatment in a subject who had HCV RNA $<$ LLOQ at Final Treatment Visit, along with the post-treatment detection of a different HCV genotype, subtype, or clade compared with baseline, as determined by phylogenetic analysis of the NS3/4A, and/or NS5A, and/or NS5B gene sequences. Reinfection in the case of the same HCV subtype is defined as a clade switch, as indicated by the lack of clustering between the baseline and post-treatment sequences by phylogenetic analysis. If phylogenetic analysis is not possible due to technical difficulties, HCV reinfection may be determined with a confirmed HCV genotype or subgenotype switch by the Versant HCV Genotype Inno-LiPA Assay v2.0 or Sanger assay.

Post-treatment relapse is defined as described earlier (**Relapse₁₂**, **Relapse₂₄**, **Relapse_{overall}**), and no genotype, subtype, or clade switch compared with baseline as determined by phylogenetic analysis of the NS3/4A, and/or NS5A, and/or NS5B gene sequences. If phylogenetic analysis is not possible due to technical difficulties, the subject will be defined as having a post-treatment relapse unless an HCV genotype or subgenotype switch is confirmed by the Versant HCV Genotype Inno-LiPA Assay v2.0 or Sanger assay.

Reasons for SVR₁₂ Non-Response

Subjects who do not achieve SVR₁₂ (SVR₁₂ non-responders) will be categorized as having:

1. On-treatment virologic failure;
2. HCV reinfection;

3. Relapse₁₂;
4. Prematurely discontinued study drug with no on-treatment virologic failure (defined as any SVR₁₂ non-responder who prematurely discontinued study drug [study drug duration < 77 days for Arm A, or < 103 days for Arm B] and did not meet the **On-treatment virologic failure or HCV reinfection** definitions);
5. Missing follow-up data in the SVR₁₂ window (defined as any subject who completed study drug without data in the SVR₁₂ window after applying the imputation rules and not meeting the definitions of [1], [2], [3], or [4]);
6. Other (defined as any SVR₁₂ non-responder not meeting the definitions of [1] – [5]).

Reasons for SVR₂₄ Non-Response

Subjects who do not achieve SVR₂₄ (SVR₂₄ non-responders) will be categorized as having:

1. On-treatment virologic failure;
2. HCV reinfection;
3. Relapse₁₂;
4. Relapse₂₄;

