10.7 Additional Efficacy Analyses

The following additional efficacy endpoints will be summarized for the ITT population:

- The percentage of subjects with HCV RNA $<$ LLOQ at each post-baseline visit in the Treatment Period (using data as observed);
- The percentage of subjects with SVR₄;
- The percentage of subjects with SVR₂₄;
- The percentage of subjects who relapse after achieving SVR₁₂ (**Relapse₂₄**).
- The percentage of subjects with virologic failure through Post-Treatment Week 24 (i.e., the SVR₂₄ non-responders due to **on-treatment virologic failure** or **Relapse_{overall}**).

For each of the above endpoints, a two-sided 95% CI using Wilson's score method will be calculated along with the number and percentage of subjects. Imputations for missing data will be performed as described in Section 6.3 for all the additional endpoints listed above except the first one.

For the ITT population, a summary of the subjects who completed treatment and relapsed (defined as **Relapse_{overall}**) will be prepared displaying the number of subjects relapsing at any timepoint and by the SVR visit window where the first relapse occurred (within the SVR₄, SVR₁₂, or SVR₂₄ window or after the SVR₂₄ window); subject numbers will be listed. A similar summary will be prepared for subjects who prematurely discontinued treatment and relapsed after having HCV RNA $<$ LLOQ at their Final Treatment Visit.

The number and percentage of subjects who do not achieve SVR₂₄ will be summarized by reason for non-response (as defined in Section 10.1) for the ITT population. A listing of subject numbers and reason for non-response will be prepared.

The concordance between SVR₁₂ and SVR₂₄ will be assessed for the overall population (across genotype and treatment arm) by the agreement between SVR₁₂ and SVR₂₄ and the positive predictive value (PPV) and negative predictive value (NPV) of SVR₁₂ on SVR₂₄. The agreement between SVR₁₂ and SVR₂₄ is a percentage defined as the number of subjects achieving both SVR₁₂ and SVR₂₄ and the number of subjects where both SVR₁₂ and SVR₂₄ are not achieved. The PPV of SVR₁₂ on SVR₂₄ is the proportion of subjects who achieve SVR₂₄ out of all subjects who achieved SVR₁₂. The NPV of SVR₁₂ on SVR₂₄ is the proportion of subjects who do not achieve SVR₂₄ out of all subjects who did not achieve SVR₁₂. Similarly, the concordance between SVR₄ and SVR₁₂ will be summarized for the overall population.

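### mITT-VF drops early discontinuers whose baseline virus returns but keeps those who are cured, so any such subject biases its SVR12 rate upward

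*SAP*

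**What the plan says.** SAP 10.1 defines virologic failure as on-treatment virologic failure or Relapse_overall. Relapse12 and Relapse_overall both require a subject with "HCV RNA < LLOQ at Final Treatment Visit who completed treatment, excluding reinfection". Completion means at least 77 days of study drug in Arm A and at least 103 days in Arm B. Protocol 5.4.1.1 and 8.1.2.2 carry the same restriction.

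Among the reasons for SVR12 non-response in SAP 10.1, the fourth begins "Prematurely discontinued study drug with no on-treatment virologic failure (defined as any". It goes on to take in every early-stopping SVR12 non-responder who meets neither the on-treatment failure nor the reinfection definition. Whether the virus came back after treatment plays no part in it.

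SAP 5.1.2 defines mITT-VF as the ITT population "modified to exclude subjects who do not achieve SVR₁₂ for reasons other than virologic failure". That population is used for the sensitivity analysis of SVR12 (SAP 10.5) and for Analysis 2 of the HCV resistance analyses (SAP 10.8.1).

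SAP 10.7 separately plans a summary for "subjects who prematurely discontinued treatment and relapsed after having HCV RNA $<$ LLOQ at their Final Treatment Visit".

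**The concern.** Among early stoppers who were below LLOQ when they stopped, the outcome decides who stays in mITT-VF. The cured subject is kept as a success, and the subject whose baseline strain is shown to have returned is removed. A population meant to isolate virologic outcomes should not lose a subject whose failure is plainly virologic.

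Two uses are exposed. mITT-VF is the only alternative population offered in support of the primary SVR12 result. It is also the basis for comparing SVR12 with and without baseline polymorphisms. SAP 4.3 says that the number of SVR12 "non-responders is expected to be less than 5", so losing even one failure matters to that comparison.

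**Working it through.** **Step 1. How early stoppers are classified.** Take Arm B subjects with fewer than 103 days of drug, for example stopping on Day 100 of 112.

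| Course after stopping early | Status under SAP 10.1 | mITT-VF |
|---|---|---|
| Below LLOQ at Final Treatment Visit, SVR12 reached | Responder (SVR12 has no minimum duration) | Kept, success |
| At or above LLOQ at end of treatment, at least 36 days of drug | EOT failure, hence virologic failure | Kept, failure |
| Below LLOQ at Final Treatment Visit, baseline strain confirmed at Post-Treatment Weeks 4 and 12 | Not a completer, so neither Relapse12 nor Relapse_overall; category 4 | Dropped |

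The third subject is one whom SAP 10.7 describes as relapsed.

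**Step 2. Inputs.** The planned sizes are 5, 45 and 50 (SAP 4.2: "Arm A will enroll approximately 5 subjects, and Arm B will enroll approximately 45 subjects"). Intervals are two-sided 95% (Protocol 8.1: "All confidence intervals will be two-sided with an alpha level of 0.05"). The number of early stoppers who relapse, *e*, is not given in the documents. I assume 0 to 3. I also assume that no one else is excluded from mITT-VF.

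**Step 3. Reproduce the plan's own figures.** The Wilson interval for x successes in n, with p = x/n and z = 1.96, is

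[p + z²/(2n) ± z·√(p(1−p)/n + z²/(4n²))] / (1 + z²/n).

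For 42/45 the centre is (0.9333 + 0.0427)/1.0854 = 0.8993 and the half-width is 0.0778. That gives 82.1% to 97.7%, the entry in SAP Table 3 for three failures in Arm B. All 15 intervals in that table reproduce to 0.1 point.

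**Step 4. Effect on the rate.** Let *v* be the subjects the SAP already counts as virologic failures.

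- As written: (N − v − e)/(N − e)
- Early relapsers counted as failures: (N − v − e)/N
- Difference: e(N − v − e)/[N(N − e)]

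The difference is positive whenever e > 0 and anyone responds, so the direction is fixed.

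| N | v | e | As written (Wilson 95%) | Relapsers counted (Wilson 95%) | Difference, points |
|---|---|---|---|---|---|
| 45 | 2 | 0 | 43/45 = 95.6% (85.2–98.8) | 43/45 = 95.6% (85.2–98.8) | 0 |
| 45 | 2 | 1 | 42/44 = 95.5% (84.9–98.7) | 42/45 = 93.3% (82.1–97.7) | 2.1 |
| 45 | 2 | 2 | 41/43 = 95.3% (84.5–98.7) | 41/45 = 91.1% (79.3–96.5) | 4.2 |
| 50 | 0 | 1 | 49/49 = 100% (92.7–100) | 49/50 = 98.0% (89.5–99.6) | 2.0 |
| 50 | 0 | 3 | 47/47 = 100% (92.4–100) | 47/50 = 94.0% (83.8–97.9) | 6.0 |
| 50 | 1 | 1 | 48/49 = 98.0% (89.3–99.6) | 48/50 = 96.0% (86.5–98.9) | 2.0 |
| 5 | 0 | 1 | 4/4 = 100% (51.0–100) | 4/5 = 80.0% (37.6–96.4) | 20.0 |

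With v = 0 the rate as written is 100% however many early stoppers relapse.

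**Step 5. What drives the gap.** Take N = 50, v = 1, one relapsed and one cured early stopper. As written the rate is 48/49 = 98.0%. Excluding both early stoppers gives 47/48 = 97.9%. Counting the relapse gives 48/50 = 96.0%. The gap therefore comes from not counting the relapse, and hardly at all from keeping the cured subject.

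**The case against.** The case for leaving the definition alone has several sound parts.

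- **The primary result is safe.** In ITT these subjects are SVR12 failures. A reader might infer that the headline efficacy estimate is inflated, but the SAP does not support that. There is also no test to distort: "No formal hypothesis will be tested in this study".
- **Nothing is hidden.** The subjects appear in the reasons-for-non-response summary and listing (SAP 10.3), the listing of mITT-VF exclusions (10.5) and the early-stopper relapse summary (10.7). The alternative rate can be rebuilt by hand.
- **The SAP does not depart from the protocol.** The completers-only rule is in both documents. Section 10.1 does not itself label category 4 as non-virologic. That status follows from its virologic failure definition read with 5.1.2, and from 10.8.1, which speaks of non-virologic failure reasons under 10.1. Section 10.7 can fairly be read as deliberate separate reporting, so calling it a flat contradiction goes too far.
- **The resistance loss is confined to Analysis 2.** The subjects' post-treatment samples at or above 1000 IU/mL are still sequenced, and Analyses 1 and 3 still include them.
- **The frequency is unknown.** The protocol reports 2 of 274 stopping for adverse events (Section 3.0) and 1 of 34 stopping at Week 4 (5.6.4.2). It is tempting to scale these to 50 subjects, but they are rates of stopping, not of stopping and then relapsing. The arm of 34 also belongs to one of the two studies behind the 274. Its early stopper had no detectable virus on stopping, and Table 6 reports 100% SVR12 for that arm.
- **Some dependence on outcome is built in.** Any population that removes only non-responders has it.

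These points limit the weight of the concern. They do not answer it, because a proven return of the baseline strain is still removed from a population defined around virologic failure.

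**Conclusion.** The point holds for the mITT-VF sensitivity analysis and resistance Analysis 2, and for nothing else. If any early stopper relapses after being below LLOQ at the Final Treatment Visit, mITT-VF overstates SVR12 by about 2 points per subject in Arm B or overall. In Arm A the first such subject moves the rate by 20 points when there is no other failure. A shift of 2 points is small beside Wilson intervals about 14 to 16 points wide (42/44 and 42/45 above), but it always goes the same way. The size rests on an assumed number of such subjects. If there are none, there is no effect. The change is worth making because it is cheap and uses data already collected.

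**What to change.** Make the change in SAP 5.1.2, and make it additive:

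1. Keep in mITT-VF everyone who is a virologic failure under SAP 10.1. This includes a single breakthrough value followed by loss to follow-up, and a completer whose last post-treatment value is at or above LLOQ without confirmation. A rule that kept only non-responders with confirmed post-treatment viremia would drop these true failures and bring back an upward bias.
2. In addition, for mITT-VF only, count as virologic failures the early discontinuers from the SAP 10.7 summary who meet all of the following: HCV RNA below LLOQ at the Final Treatment Visit; then HCV RNA at or above LLOQ by the end of the SVR12 window, either confirmed or as the last available value; and not a reinfection.
3. Use the same population in SAP 10.8.1 Analysis 2.
4. Leave the completers-only Relapse12 secondary endpoint unchanged, so it still matches the protocol.

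Subjects with under 36 days of drug who are at or above LLOQ at end of treatment without breakthrough also fall in category 4, and this change does not reach them. The SAP should state how they are handled.

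The cost is a few lines of SAP text and one derivation flag, with no new data. The mITT-VF rate may come out slightly lower and will differ a little from the sponsor's standard definition.

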10.2 Handling of Multiplicity

No multiplicity adjustment is needed for this study because there is no hypothesis testing.

10.3 Primary Efficacy Analysis

The primary efficacy endpoint is SVR₁₂ (HCV RNA < LLOQ 12 weeks after the last actual dose of study drug). The number and percentage of subjects in the ITT population achieving SVR₁₂ will be calculated along with a two-sided 95% CI using the normal approximation to the binomial distribution, unless the number of SVR₁₂ non-responders is less than 5, where the Wilson's score method¹ will be used to calculate the CI instead.

A summary of reasons for SVR₁₂ non-response (e.g., on-treatment virologic failure, relapse, other) will be provided. A listing of subjects who do not achieve SVR₁₂ by reason for non-response will also be provided.

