3.2 Benefits and Risks

Benefits

Subjects who have experienced virologic failure following treatment with ABT-493/ABT-530, as well as treatment with 3D or 2D, are difficult patient populations to cure and need effective and safe options for retreatment. Study M15-942 is designed to retreat these subjects with an intensified regimen that contains ABT-493, an NS3/4A inhibitor; ABT-530, an NS5A inhibitor; SOF, an NS5B inhibitor and RBV, for either 12 weeks or 16 weeks.

One of the potential benefits of retreatment with ABT-493/ABT-530 plus SOF and RBV is that the co-administration of drugs of distinct mechanisms of action can potentially inhibit the viral replication of HCV variants present in DAA treatment-experienced subjects effectively, thus leading to a higher cure rate.

ABT-493/ABT-530 demonstrates excellent antiviral activity with high genetic barrier to development of drug resistance which has been translated into high SVR₁₂ rates in clinical studies.

The addition of SOF and RBV to ABT-493/ABT-530 provides additional mechanism(s) of action that may overcome resistant variants selected in subjects exposed to ABT-493/ABT-530 alone. The longer treatment duration of 16 weeks for cirrhotic subjects, subjects with GT3 infection, and subjects who have previously failed a PI-

and/or NS5Ai-containing regimen before experiencing virologic failure in an AbbVie HCV parent study is expected to improve the chances of achieving SVR₁₂.

SVR rates among HCV/HIV-1 co-infected patients treated with new, all-oral HCV DAA regimens are comparable to those observed in HCV-monoinfected patients, and this similar efficacy finding is anticipated following treatment with ABT-493/ABT-530. In addition, successfully treating these patients is expected to address the risk of increased disease progression in untreated HCV/HIV-1 co-infected patients (accelerated hepatic fibrosis progression and higher rates of liver decompensation and death compared to HCV monoinfection). Also, liver disease is a leading cause of non-AIDS-related mortality among HIV-1-infected patients.²⁵⁻²⁷

Risks

The likelihood of successfully retreating HCV infection with ABT-493/ABT-530 plus SOF and RBV is not known.

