8.1.2.1 Primary Efficacy Endpoints

The primary efficacy endpoint is the percentage of subjects in the ITT population who achieve SVR₁₂ (HCV RNA < LLOQ 12 weeks after the last actual dose of study drug), by treatment arm and overall. The number and percentage of subjects achieving SVR₁₂ will be summarized along with a two-sided 95% confidence interval using the normal approximation to the binomial distribution, unless the number of virologic failures is less than 5, then the Wilson's score method will be used for the confidence interval instead.

A summary of reason for SVR₁₂ non-response (e.g., OTVF, relapse, other) will be provided.

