10.5 Sensitivity Analyses for SVR

As sensitivity analyses, the number and percentage of subjects in the mITT-VF population achieving SVR₁₂ will be summarized along with two-sided 95% CIs using the normal approximation to the binomial distribution and the Wilson's score method.

A different CI from that used for the primary analysis will be calculated for the primary endpoint of SVR₁₂ based on the ITT population as a sensitivity analysis. If the number of SVR₁₂ non-responders is ≥ 5 , then the two-sided 95% CI using Wilson's score method will be calculated. If the number of SVR₁₂ non-responders is < 5 , the two-sided 95% CI using the normal approximation to the binomial distribution will be calculated.

Listings of subjects excluded from the mITT-VF population will be provided, as applicable.

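### The primary SVR12 interval changes method at five failures, so in Arm B and overall one more failure raises both limits, and the protocol and SAP count different failures to trigger the change

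*SAP*

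**What the plan says.** SAP 10.3 reports SVR12 in the ITT population with a 95% interval from the normal approximation, "unless the number of SVR₁₂ non-responders is less than 5"; below that count the Wilson score interval replaces it. Protocol 8.1.2.1, and the synopsis in the same words, has the same cut-off but a different count: "unless the number of virologic failures is less than 5, then the Wilson's score method will be used for the confidence interval instead".

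SAP 4.3 expects Wilson to apply "because the number of SVR₁₂ non-responders is expected to be less than 5", and its Table 3 gives Wilson limits for 0 to 4 failures in Arm A, Arm B and overall. It states no assumed SVR12 rate.

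For the ITT sensitivity interval, SAP 10.5 takes whichever method was not primary. With five or more non-responders that is Wilson. Otherwise, "If the number of SVR₁₂ non-responders is < 5 , the two-sided 95% CI using the normal approximation to the binomial distribution will be calculated". Protocol 8.1.2.3 instead gives Wilson as the ITT sensitivity interval whatever the count.

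SAP 12.1 lists nine changes from the protocol. Neither the new trigger nor the changed sensitivity rule is among them.

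**The concern.** The study tests no hypothesis, so the SVR12 rate and its interval are the whole primary efficacy result. An interval for a proportion should move down when one more subject fails. A rule that changes method at a fixed count can break that property at the step, and Table 3 ends one count short of it.

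The two triggers also count different things. SAP 10.1 limits virologic failure to on-treatment failure or relapse. Its list of reasons for SVR12 non-response adds reinfection, premature discontinuation, missing follow-up data and other. Whenever a subject falls into one of those added categories, the two documents can require different primary intervals from the same data.

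**Working it through.** **Inputs.** Level: "All confidence intervals will be two-sided with an alpha level of 0.05" (Protocol 8.1), so z = 1.95996 and z² = 3.8415. Sizes: "Arm A will enroll approximately 5 subjects, and Arm B will enroll approximately 45 subjects" (SAP 4.2), total 50. I read the trigger as applied to each arm and to the total separately, as the layout of Table 3 suggests.

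**Formulas**, with p the observed SVR12 proportion:
- Wilson: centre (p + z²/2n)/(1 + z²/n), half-width z·√(p(1−p)/n + z²/4n²)/(1 + z²/n).
- Normal approximation: p ± z·√(p(1−p)/n).

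**Reproducing Table 3.** For 46/50, z²/n = 0.0768. The centre is (0.92 + 0.0384)/1.0768 = 0.8900. The half-width is 1.95996 × √(0.001472 + 0.000384)/1.0768 = 0.0784. The interval is 81.2–96.8%, as printed. All 15 entries of Table 3 reproduce to one decimal.

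**The step from four to five failures.** For 45/50 the normal approximation is 0.90 ± 1.95996 × √(0.09/50) = 0.90 ± 0.0832, or 81.7–98.3%. For 40/45 the standard error is 0.0468 and the interval 79.7–98.1%.

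| Group | 4 failures: estimate, primary (Wilson) | 5 failures: estimate, primary (normal) | 5 failures, Wilson |
|---|---|---|---|
| Overall, N=50 | 92.0%, 81.2–96.8% | 90.0%, 81.7–98.3% | 78.6–95.7% |
| Arm B, N=45 | 91.1%, 79.3–96.5% | 88.9%, 79.7–98.1% | 76.5–95.2% |
| Arm A, N=5 | 20.0%, 3.6–62.4% | 0%, 0–0% | 0–43.4% |

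Overall, the estimate falls 2.0 points while the lower limit rises 0.5 and the upper 1.5. In Arm B the estimate falls 2.2 points while the limits rise 0.4 and 1.6. Checking every N from 5 to 59, both limits rise from N=34 upwards, so modest over- or under-enrolment does not remove the effect overall or in Arm B. In Arm A the limits do not rise. There the fault is that p = 0 makes the standard error zero.

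**The two triggers on one data set.** Take 50 subjects, 45 with SVR12, 4 virologic failures and 1 with no SVR12 value after imputation, counted as a failure under SAP 6.3. The protocol counts 4 and requires Wilson, 78.6–95.7%. The SAP counts 5 and requires the normal approximation, 81.7–98.3%.

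**How likely is the step to matter?** The probability of five or more non-responders is 1 − Σ (k = 0 to 4) C(n,k)(1−π)^k π^(n−k), where π is the true SVR12 rate. The documents give no π, and Protocol 3.2 says: "The likelihood of successfully retreating HCV infection with ABT-493/ABT-530 plus SOF and RBV is not known". Under assumed rates:

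| Assumed true SVR12 | 97% | 95% | 92% | 90% |
|---|---|---|---|---|
| N=50 | 1.7% | 10% | 37% | 57% |
| N=45 | 1.1% | 7% | 29% | 47% |

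**The case against.** The best defence is that little is lost. The rule is fixed in advance and depends only on the count, so no analyst has a choice to make. SAP 10.5 reports Wilson on the same ITT population whenever five or more subjects fail, and Protocol 8.1.2.3 also provides it. No hypothesis is tested, and neither document names a threshold that the lower limit must clear. The SAP also expects fewer than five non-responders, in which case Wilson is primary. All of this stands, and it limits the point to which interval carries the primary label.

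A reader might go further and infer that the reported lower limit would be about 3 points too high. The calculations do not support that. Three points is the distance from Wilson, not an error against the true rate. Averaged over true SVR12 from 80% to 98%, the switching rule covers 97.5% (N=50) and 97.8% (N=45), against 95.4% and 95.5% for Wilson throughout, so it is conservative on average. The exception is local: at N=50 coverage drops to about 91% near a true rate of 81%.

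A reader might also infer that the reversal affects every arm, or that the method is picked at will after the data are seen. Arm A shows no reversal, and the rule leaves no discretion.

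The defence does not answer two things. The secondary endpoints, subgroups, SVR4 and SVR24 all use Wilson without a trigger (SAP 10.4, 10.6, 10.7), so 45/50 at both time points would be printed as 81.7–98.3% for SVR12 and 78.6–95.7% for SVR24. And the amendment rationale in Protocol 1.1 says a regulator asked for Wilson when SVR12 is high but below 100%. At 45/50 the SAP still puts the normal approximation first.

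**Conclusion.** The point holds as a should-fix matter of coherence and consistency. For Arm B and overall, the primary interval moves up by about half a point at the lower limit and 1.5 points at the upper when the fifth subject fails, and then sits about 3 points above Wilson at its lower end. In Arm A, 5/5 failures give a primary interval of no width. The protocol and SAP trigger the switch on different counts, and SAP 12.1 does not declare it, so the headline interval can depend on which document is followed.

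This rests on the planned sizes of 5, 45 and 50 and on applying the trigger within each group. How often it would matter depends on an SVR12 rate that the documents do not give: at N=50, from 1.7% of trials if the true rate is 97% to 57% if it is 90%. Wilson is reported in every case, so no information is withheld and no formal conclusion changes.

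**What to change.** In SAP 10.3, Protocol 8.1.2.1 and the protocol synopsis, use the Wilson score interval for SVR12 in each arm and overall at every failure count, and delete the trigger. Both limits then fall with each extra failure: overall from 81.2–96.8% at four to 78.6–95.7% at five.

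In SAP 10.5, name one ITT sensitivity method that does not depend on the count. If it is the normal approximation, the authors should know that at N=45 and N=50 it has zero width with no failures and passes 100% with one to three. An exact interval would avoid this but is not needed to cure the fault. Extending Table 3 past four failures is likewise optional.

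Record the change from the protocol in SAP 12.1, and settle it before database lock, so that the choice cannot depend on the count.

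The cost is a few lines of wording and almost no programming, since Wilson is already needed for the other endpoints. The one visible consequence is a headline lower limit about 3 points lower at five failures (3.0 overall, 3.2 in Arm B).
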